5.6.3 Premature Study Withdrawal

Patients are considered to be withdrawn prematurely from the study if they do not complete the follow-up visits until Study Day 29.

A patient may voluntarily discontinue participation in this study at any time. The investigator may also, at their discretion, discontinue the patient from participating in this study at any time. Patients may be prematurely discontinued from the study for any of the following reasons:

- Adverse event
- Protocol deviation
- Study closed/terminated
- Loss to follow-up
- Consent withdrawal
- Study or investigator non-compliance
- At the request of the investigator

- Pregnancy

Patients are not obligated to state the reason for withdrawal from this study. However, the reasons for withdrawal, or failure to provide a reason, must be documented by the investigator on the Completion/Withdrawal section of the eCRF.

If a patient is withdrawn from the study for any reason, the investigator must make every effort to perform the study evaluations for Withdrawal visit as specified in the [Table 6-1](#). Withdrawn patients will not be replaced.

5.6.4 Withdrawal of informed consent

Patients/subjects may voluntarily withdraw consent to participate in the study for any reason at any time. Withdrawal of consent (WoC) from the study occurs only when a subject:

- Does not want to participate in the study anymore

and

- Does not allow further collection of personal data

In this situation, the investigator should make a reasonable effort (e.g., telephone, e-mail, letter) to understand the primary reason for the patient's decision to withdraw his/her consent and record this information.

Study treatment must be discontinued and no further assessments conducted, and the data that would have been collected at subsequent visits will be considered missing.

Further attempts to contact the patient are not allowed unless safety findings require communicating or follow-up.

All efforts should be made to complete the assessments prior to study withdrawal. A final evaluation at the time of the patient's study withdrawal should be made as detailed in the assessment table.

Novartis will continue to keep and use collected study information (including any data resulting from the analysis of a patient's samples until their time of withdrawal) according to applicable law.

All biological samples not yet analyzed at the time of withdrawal will no longer be used, unless permitted by applicable law. They will be stored according to applicable legal requirements.

5.6.5 Loss to follow-up

For subjects whose status is unclear because they fail to appear for study visits without stating an intention to discontinue or withdraw, the investigator must show "due diligence" by documenting in the source documents steps taken to contact the subject, e.g., dates of telephone calls, registered letters, etc. A patient cannot be considered as lost to follow-up until the time point of his/her scheduled end of study visit has passed.

5.6.6 Early study termination by the sponsor

The study can be terminated by Novartis at any time for any reason. This may include reasons related to the benefit risk assessment of participating in the study, practical reasons, or for regulatory or medical reasons (including slow enrolment). Should this be necessary, the patient

must be seen as soon as possible and treated as a prematurely withdrawn patient. The investigator may be informed of additional procedures to be followed in order to ensure that adequate consideration is given to the protection of the patient's interests. The investigator will be responsible for informing the Institutional Review Board/Independent Ethics Committee (IRBs/IECs) of the early termination of the trial.

6 Visit schedule and assessments

Patients must be seen for all visits on the designated day, or as close to it as possible. Missed or rescheduled visits should not lead to automatic discontinuation. Patients who prematurely discontinue the study for any reason should be scheduled for a visit as soon as possible, at which time all of the assessments listed for the final visit will be performed. At this final visit, all dispensed investigational product should be reconciled and the adverse event and concomitant medications reconciled on the eCRF.

EOT = End of treatment; UNS = Unscheduled visit; PSW = Premature study withdrawal

X = assessment to be recorded on clinical data base

S = assessment to be recorded on source documentation only

β -hCG = The β -subunit of human Chorionic Gonadotropin

¹ Visit structure given for internal programming purpose only.

² Prior to start of any study procedure.

³ Commencement of rescue medication with Coartem may occur after start of trial medications and up to Study Day 28 as deemed necessary by the investigator. Any patient on KAE609 who have not been rescued till Study Day 28, will be given Coartem at end of the study at Study Day 29.

⁴ A complete physical examination will be performed by the investigational staff *at screening* and include the examination of general appearance, skin, neck (including thyroid), eyes, ears, nose, throat, lungs, heart, abdomen including splenomegaly, back, lymph nodes, extremities, vascular and neurological. Body height and body weight will also be measured at screening and data recorded on clinical data base.

An abbreviated physical examination will be performed at all other visits starting from Study Day 1. An abbreviated physical exam will include the examination of general appearance, vital signs (blood pressure and pulse) and body temperature. Fever monitoring will be done until resolution of fever, defined as being afebrile for 48 hours.

Body weight will also be measured at Study End (Study Day 29 or earlier in case of premature patient discontinuation) and data recorded on clinical data base.

⁵ Laboratory tests should also be taken at any time of withdrawal/discontinuation.

⁶ Missed PK sampling time should be taken as soon as possible and actual time should be recorded. **For Scheduled time ≤ 2 h \pm 10 min; 2 - ≤ 24 h \pm 30 min; > 24 - ≤ 72 \pm 2 h, > 72 h \pm 24 h.**

⁷ Will be repeated in case of abnormalities.

⁸ The patient's menstrual and contraceptive history will be taken and a serum/plasma β -hCG pregnancy test will be performed at screening to exclude pregnancy. A urine β -hCG test will be performed at end of study. Results must confirm negative **before** dosing.

⁹ Meals consumed within 30 min prior to dosing and 4 hours post dosing to be documented for Coartem cohort.

¹⁰ Comparator only (Coartem).

¹¹ Not applicable to 1-day treatment regimen.

¹² ECG's should be taken in triplicate within 5 min after resting for at least 10 min in the supine position to ensure a stable heart rate according to the ECG investigator manual. Also, ECG's should be taken before any other procedure taken at the same nominal time point is performed. **For Scheduled time ≤ 2 h \pm 10 min; 2 - ≤ 24 h \pm 30 min; > 24 - ≤ 72 \pm 2 h, > 72 h \pm 24 h.**

6.1 Information to be collected on screening failures

All patients/subjects who have signed informed consent but not entered into the next period will have the study completion page for the screening period, demographics, inclusion/exclusion, and serious adverse event (SAE) data collected. Adverse events that are not SAEs will be followed by the investigator and collected only in the source data.

6.2 Patient demographics/other baseline characteristics

Patient demographic and baseline characteristic data to be collected on all patients include:

- Age
- Gender
- Body weight
- Body height
- Body temperature
- Severe malaria
- Vital signs
- Prior and concomitant medications
- Blood chemistry and hematology
- Urinalysis
- Pregnancy test
- Malaria blood film for parasite
- Blood sampling for Polymerase Chain Reaction (PCR) genotyping
- Medical history
- Triplicate 12-lead ECG

Investigators will have the discretion to record abnormal test findings on the medical history CRF whenever in their judgment, the test abnormality occurred prior to the informed consent signature.

6.3 Treatment exposure and compliance

All study treatment taken must be recorded in the Drug Administration Record (DAR) CRF, along with any comments about whether the patients swallowed all or part of the medication, whether and when vomiting occurred, and whether replacement medication had to be initiated.

Records of study medication used and exact dosages administration will be kept during the study. Drug accountability will be noted by the field monitor during site visits and at the completion of the study.

All medication (other than study drug) and significant non-drug therapies administered after the patient starts treatment with study drug will be documented on the concomitant medications/Significant non-drug therapies (surgical and medical procedures CRF and non-surgical procedures CRF) CRF after start of study drug.

6.4 Efficacy

Efficacy assessments will be based on the PCR-corrected Adequate Clinical and Parasitological Response (ACPR) and PCR-Uncorrected ACPR at Study Days 15 and 29 (see [Section 6.5.8](#)).

6.4.1 Parasitaemia assessment

Blood sampling for parasitology can be done by means of finger prick except when the timing for parasitology assessments coincide with time for clinical laboratory tests, in which case, blood sample can be taken from the venous blood collected for clinical laboratory analyses.

Parasite counts:

- Giemsa stained thick (and thin) films will be examined. Thin films will be examined only if identification of species is needed after malaria (*Plasmodium*) parasite is detected in a thick film
- Examination with binocular microscope and with oil immersion lens
- Screening examination (prior to patient inclusion into the trial), thick film:
 - at least 200 thick film fields are examined. If there is no malaria parasite, the slide is declared negative, and the patient is not suitable for inclusion.
 - if asexual forms of Plasmodia are found, a total of 200 thick film fields are to be screened for *Plasmodium* species other than *P. falciparum*.
 - when it has been ascertained that *P. falciparum* is present, a count is made of the asexual forms against leukocytes, using a tally counter. Counting needs to be done based on at least 200 leukocytes according to the WHO standards. If less than 100 parasites, counting will be extended to 500 leukocytes. The parasite density will be calculated according to the formula:

$$\text{Parasite density per } \mu\text{l} = \frac{\text{Number of } Plasmodium \text{ parasites} \times \text{actual leukocytes (White Blood Cell, WBC)}}{\text{Number of leukocytes (WBC) counted (200)}}$$

- Blood examination during the 29 day trial period:
 - a total of 200 thick films fields are examined (tally counter) before a slide can be pronounced negative
 - if asexual forms of *P. falciparum* are present, a parasite count is required
 - if *Plasmodium* species other than *P. falciparum* are found, note species

The **count should be made for each species** ([White et al 2014](#)). Blood film may be potentially confirmed by PCR. Thick (and thin blood) films will be taken as specified in the assessment schedule table and evaluated by standard techniques (Giemsa stain). This will be the definitive test for a positive *P. falciparum* infection. The parasite counts can also be quantified in ‰ (per 1000) of red cells in the thin film.

Further technical details are provided in the laboratory manual.

6.4.2 Appropriateness of efficacy assessments

The microscopy examination methods to quantify the malaria parasite in blood are validated methods ([Sinden et al 2012](#); [White et al 2014](#)). For full details refer to the Study Laboratory Procedures Manual.

6.5 Safety

Clinical adverse events will be monitored throughout the study to assess the general safety and tolerability of the treatment groups.

6.5.1 Physical examination and malaria signs and symptoms

A *complete* physical examination will be performed by the investigational staff *at screening* and include the examination of general appearance, skin, neck (including thyroid), eyes, ears, nose, throat, lungs, heart, abdomen including splenomegaly, back, lymph nodes, extremities, vascular and neurological.

An *abbreviated* physical examination will be performed at all other visits starting from Study Day 1 including the examination of general appearance and vital signs. Fever monitoring will be done until resolution of fever, defined as being afebrile for 48 hours.

A full assessment of *malaria signs and symptoms* will be made alongside the physical examinations at timepoints described in the assessment schedule for all patients ([Table 6-1](#)).

Information for all physical examinations must be included in the source documentation at the study site. Body height and body weight must be recorded in the clinical database. Clinically relevant findings that are present prior to signing informed consent must be included in the Medical History part of the eCRF. Significant findings made after first administration of investigational drug which meet the definition of an Adverse Event must be recorded on the Adverse Event section of the eCRF.

6.5.2 Vital signs

Vital signs (blood pressure, body pulse) will be monitored as part of the physical exam as indicated in the study assessment schedule table and recorded on the clinical database.

After the patient has been in supine position for five minutes, systolic and diastolic blood pressure will be measured three times using an automated validated device, e.g., OMRON, with an appropriately sized cuff. The repeat measurements will be made at 1 - 2 minute intervals and the mean of the three measurements will be used. The same arm must be used throughout the study. A sphygmomanometer with an appropriately sized cuff should be used.

6.5.3 Height and weight

In addition, body height in centimeters (cm) will be measured at screening and body weight to the nearest 0.1 kilogram (kg) in indoor clothing, but without shoes will be measured at screening and at study end (Study Day 29 or earlier in case of premature patient withdrawal from study participation).

6.5.4 Laboratory evaluations

A local laboratory will be preferably used for analysis of all specimens collected except for PCR (parasite identification), ECG and PK measurements where central laboratory will be used. Details on the collections, shipment of samples and reporting of results by the central laboratories are provided to investigators in the laboratory manuals where applicable. Assessments will be done as indicated in the study assessment schedule table.

Clinically notable laboratory findings are defined in [Appendix 1](#).

Hematology, Blood chemistry and Urinalysis assessments will be done as described in the assessment schedule table ([Table 6-1](#)).

6.5.4.1 Hematology

Hemoglobin, hematocrit (packed-cell volume (PCV)), platelets, white blood cell (WBC) count with differential (as much as possible, neutrophil, lymphocyte and eosinophils counts will be performed while basophils and monocytes can be aggregated as 'other') counts will be measured. Red blood cell count (RBC), reticulocytes count will be performed in case of significant hemoglobin drop > 2 g/dL or hemoglobin levels ≤ 5 g/dL (will be optional depending on site equipment). Assessments will be done as indicated in the study assessment schedule table ([Table 6-1](#)).

6.5.4.2 Blood chemistry

Routine blood chemistry testing will be performed according to the visit schedule in order to monitor the general medical condition of the patient.

This includes: Glucose, creatinine (serum), transaminases (ALT/SGPT and AST/SGOT), serum- γ -glutamyl transferase (GGT), Total and conjugated bilirubin, haptoglobin, LDH, ALP, BUN, INR, sodium, potassium, magnesium, calcium, chloride, total protein and, albumin, .

6.5.4.3 Urinalysis

Dipstick measurements for specific gravity, protein, glucose and blood will be performed as indicated in the study assessment schedule table. Microscopy will be performed and urine sediment will be assessed in case of an abnormal dipstick test.

6.5.5 Electrocardiogram (ECG)

ECGs should be taken in triplicate within 5 minutes (after 10 minutes rest in the supine position to ensure a stable heart rate according to the ECG investigator manual). The preferred sequence of cardiovascular data collection during study visits is ECG collection first, followed by vital signs, and blood sampling.

The Fridericia QT correction formula (QTcF) should be used for clinical decisions.

Triplicate 12 lead ECGs are to be collected with ECG machines supplied by the central laboratory. Initial manual readout will be done locally in order to detect significant safety findings and allow for immediate response if needed. Local readout will be used for inclusion/exclusion purposes as central readout is not available within 24 hours.

In the event that a clinically significant ECG abnormality is identified at the site (e.g., severe arrhythmia, conduction abnormality of QTcF > 500 ms) the SAE must be reported according to the procedure described in [Section 7.2](#). If the patient is hemodynamically compromised, the investigator or a medically qualified person must initiate appropriate safety procedures without delay (for example cardioversion).

If QTcF is > 500 ms or QTcF increases ≥ 60 ms from baseline occur at any time, the patient should be assessed at the site and appropriate safety procedures (e.g., electrolyte correction) initiated without delay, if required. In addition two additional ECGs should be collected at 2-min intervals and provided to the central ECG laboratory for confirmation.

Clinically significant abnormalities must be recorded on the relevant section of the medical history/Current medical conditions/AE eCRF page as appropriate.

For 3 day regimens, any post-dose average QTc ≥ 500 ms will result in patient discontinuation from the treatment if there is a planned subsequent treatment.

Assessments will be done as indicated in the study assessment schedule table. All ECGs will be assessed centrally by an independent and blinded (with age of patient identified) cardiologist.

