5.5.4 Instructions for prescribing and taking study treatment

KAE609

KAE609 can be administered irrespective of the timing of food intake.

Study medication will be administered by the study center personnel with approximately 180-240 ml of water. Each subject's mouth must be checked to ensure that the medication was swallowed. In the case that the patient vomits within 30 minutes of intake a replacement dose will be given to the patient and the investigator or designee will notify IRT. If the second dose is vomited the patient has to be given Coartem as rescue medication.

Coartem

Patients will be dosed BID for 3 days (at the following time points: 0, 8, 24, 36, 48, and 60 hours) and must receive a standard meal within 30 min prior to dosing, as per label. In the case that the patient vomits within 1 hour of intake a replacement dose will be given to the patient and the investigator or designee will notify IRT. If the second dose is vomited the patient has to be given non-lumefantrine standard of care.

Conventional 80/480 mg tablets or 20/120 mg tablets are to be taken orally with a glass of water. The dispersible tablet is to be dissolved in 10 mL of water in a small cup, and subsequently administered orally under hospital supervision; thereafter the cup will be rinsed with an additional 10 mL of water and the content is to be swallowed again.

Coartem medication should be followed whenever possible by food/drink (broth, sweetened condensed milk, etc.) as appropriate.

All dosages prescribed and dispensed to the subject during the study must be recorded on the Dosage Administration Record (DAR) CRF.

All kits of study treatment assigned by the IRT will be recorded in the IRT.

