5.6.2 Discontinuation of study treatment

Patients will be treated under hospital supervision during the treatment period. Discontinuation of study treatment for a patient occurs when study drug is stopped earlier than the protocol planned duration, and discontinuation can be initiated by either the patient or the investigator. For patients assigned to 1-day treatment arm, they will not be considered as treatment discontinuation if those discontinuation events occur after they have completed the treatment as assigned.

The investigator must discontinue study treatment for a given patient if, on balance, he/she believes that continuation would negatively impact the participation of the patient in the trial.

Study treatment must be discontinued under the following circumstances:

- Patient request
- Pregnancy (see [Section 6.5.6](#) and [Section 7.6](#))
- Use of prohibited treatment as per recommendations in [Section 5.5.8](#)
- Any situation in which study participation might result in a safety risk to the patient and/or any adverse events that in the judgment of the investigator, taking into account the patient's overall status, prevent the patient from continuing participation in the study
- Unsatisfactory therapeutic effect (see [Section 6.5.8](#))

- Emergence of the following adverse events: severe nausea/vomiting, severe pruritus, increases in QTcF to >500 ms (based on repeat Electrocardiograms (ECGs), development of ventricular arrhythmia or clinically significant (symptomatic) bradycardia (see [Appendix 3](#))
- Any laboratory abnormalities (e.g., LFT increase) that in the judgment of the investigator, taking into consideration the patient's overall status, prevent the patient from continuing taking the study medication (see [Appendix 2](#))
- Deviation from the planned dose regimen for the study drug

Patients who discontinue study drug for any of the above reasons may be given rescue medication at the discretion of the investigator and will be followed for the whole study duration until Study Day 29.

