- Any clinical event of jaundice (or equivalent term)
- ALT or AST $> 3 \times$ ULN accompanied by (general) malaise, fatigue, abdominal pain, nausea, or vomiting, or rash with eosinophilia
- Any adverse event potentially indicative of a liver toxicity, like hepatic failure, fibrosis and cirrhosis and other liver damage-related conditions; non-infectious hepatitis, liver neoplasms

2. Cardiac

- Absolute QTcF > 500 ms (confirmed by repeat ECGs)

14 Appendix 2: Liver event and Laboratory trigger Definitions and Follow-up Requirements

Table 14-1 Liver Event and Laboratory Trigger Definitions

	Definition/ threshold
LIVER LABORATORY TRIGGERS	
 • $3 \times \text{ULN} < \text{ALT} / \text{AST} \leq 5 \times \text{ULN}$ • $1.5 \times \text{ULN} < \text{TBL} \leq 2 \times \text{ULN}$
LIVER EVENTS (Medically significant events to be reported as SAEs)	
 • $\text{ALT or AST} > 5 \times \text{ULN}$ • $\text{ALP} > 2 \times \text{ULN}$ (in the absence of known bone pathology) • $\text{TBL} > 2 \times \text{ULN}$ (in the absence of known Gilbert syndrome) • $\text{ALT or AST} > 3 \times \text{ULN}$ and $\text{INR} > 1.5$ • Potential Hy's Law cases (defined as $\text{ALT or AST} > 3 \times \text{ULN}$ and $\text{TBL} > 2 \times \text{ULN}$ [mainly conjugated fraction] without notable increase in ALP to $> 2 \times \text{ULN}$) • Any clinical event of jaundice (or equivalent term) • $\text{ALT or AST} > 3 \times \text{ULN}$ accompanied by (general) malaise, fatigue, abdominal pain, nausea, or vomiting, or rash with eosinophilia • Any adverse event potentially indicative of a liver toxicity*

*These events cover the following: hepatic failure, fibrosis and cirrhosis, and other liver damage-related conditions; the non-infectious hepatitis; the benign, malignant and unspecified liver neoplasms
TBL: total bilirubin; ULN: upper limit of normal

Table 14-2 Follow Up Requirements for Liver Events and Laboratory Triggers

Criteria	Actions required	Follow-up monitoring
Potential Hy's Law case ^a	
 • Discontinue the study treatment immediately • Repeat LFTs within 24hHospitalize, if clinically appropriate • Establish causality • Complete liver CRF • Report to Novartis as an SAE 	ALT, AST, TBL, Alb, PT/INR, ALP and GGT until resolution ^c (frequency twice a week until resolution, stabilize or return to within baseline values)
ALT or AST		

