**Table 5-6 Analysis visit windows based on study day and time**

Analysis Visit	Analysis timepoint	Analysis window for assessment group			
		Temperature/ Parasite count	ECG		PK
			KAE609	Coartem	
Baseline	0 hrs	up to 0 hrs	up to < 0 hrs	up to < 0 hrs	NA
Day 1	1 hrs	NA	NA	NA	>0 to 1.5 hrs
	2 hrs	>0 to 3 hrs	NA	NA	>1.5 to 3 hrs
	4 hrs	>3 to 6 hrs	>0 to 8 hrs	NA	>3 to 5 hrs
	6 hrs	NA	NA	>0 to 37 hrs	>5 to 7 hrs
	8 hrs	>6 to 10 hrs	NA	NA	>7to 10 hrs
	12 hrs	>10 to 18 hrs	>8 to 18 hrs	NA	>10 to 18 hrs
Day 2	24 hrs	>18 to 30 hrs	>18 to 38 hrs	NA	>18 to 38 hrs
	36 hrs	>30 to 42 hrs	NA	NA	NA
Day 3	48 hrs	>42 to 54 hrs	NA	NA	>38 to 49 hrs

	50 hrs	NA	NA	NA	>49 to 51 hrs
	52 hrs	NA	>38 to 56 hrs	NA	>51 to 54 hrs
	56 hrs	NA	NA	NA	>54 to 58 hrs
	60 hrs	>54 to 66 hrs	>56 to 66 hrs	NA	>58 to 64 hrs
	68 hrs	NA	NA	>37 hrs to Day13	>64 to 70 hrs
Day 4	72 hrs	>66 hrs to Day 4	>66 hrs to Day 16	NA	>70 hrs to Day 6
Day 5	NA	Day 5-6	NA	NA	NA
Day 8	NA	Day 7 – 9	NA	NA	Day 7 – 9
Day 11	NA	Day 10 – 13	NA	NA	NA
Day 15	NA	Day 14 – 16	NA	NA	NA
Day 22	NA	Day 17 – 25	NA	NA	NA
Day 29/end of study	NA	Day 26 and above	Day 17 and above	Day 14 and above	NA

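### The QTc rule for stopping study treatment is stated inconsistently, and the scheduled ECGs implied by the SAP appear to leave the later doses of a 3-day regimen uncovered.

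*Protocol*

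**What the plan says.** Protocol Section 5.6.2 introduces its list with "Study treatment must be discontinued under the following circumstances". The relevant entry reads "increases in QTcF to >500 ms (based on repeat Electrocardiograms (ECGs" and refers the reader to Appendix 3.

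Protocol Section 6.5.5 has two QTc statements. The general one covers QTcF above 500 ms, or a rise of at least 60 ms from baseline, at any time. The patient is then assessed, and the text continues: "In addition two additional ECGs should be collected at 2-min intervals and provided to the central ECG laboratory for confirmation". The second is specific to 3-day regimens: an average QTc of 500 ms or more after dosing "will result in patient discontinuation from the treatment if there is a planned subsequent treatment".

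Protocol Appendix 1 lists "Absolute QTcF > 500 ms (confirmed by repeat ECGs" among the findings to be reported as serious adverse events.

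On timing, Protocol Section 5.5.4 gives Coartem at "0, 8, 24, 36, 48, and 60 hours". KAE609 in the repeated-dose arms is given once daily for three days. SAP Table 5-6 lists treatment-period ECG timepoints of 4, 12, 24, 52, 60 and 72 h for KAE609, and of 6 and 68 h for Coartem. The second Coartem window is ">37 hrs to Day13".

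**The concern.** A stopping rule should give the same answer whichever section a site opens. Here the 3-day sentence in Section 6.5.5 does not say whether the confirmation ECGs described earlier in that section must come first, while Section 5.6.2 builds the repeat into its criterion. Two sites could treat the same patient differently.

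The order matters because the next dose is at most 24 h away. The confirmation ECGs go to the central laboratory, and Section 6.5.5 says, when discussing eligibility, that central readings are not available within 24 h.

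The analysis is affected too. A KAE609 3-day patient stopped after one or two doses has taken 1/3 = 33% or 2/3 = 67% of the regimen. Both are below the 80% needed for the per-protocol and PK analysis sets.

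The second worry is reach. The 3-day rule exists to withhold a further dose, so it needs a reading taken before that dose. If the scheduled ECGs that reflect repeated dosing all come after the last dose, routine monitoring cannot trigger the rule on them.

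**Working it through.** **The statements side by side**

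| Place in protocol | Measure | Limit | Repeat or confirmation | Consequence |
|---|---|---|---|---|
| 5.6.2 | QTcF | > 500 ms | based on repeat ECGs | must stop |
| 6.5.5, general | QTcF | > 500 ms, or rise ≥ 60 ms | two further ECGs, centrally confirmed | assess patient |
| 6.5.5, 3-day regimens | average QTc | ≥ 500 ms | not stated | stop if a dose remains |
| Appendix 1 | QTcF | > 500 ms | confirmed by repeat | report as serious adverse event |

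Two illustrative patients with a dose remaining:

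- Average exactly 500 ms: 500 ≥ 500 is true, so the 3-day rule stops treatment. 500 > 500 is false, so Section 5.6.2 does not. The general paragraph of 6.5.5 would not ask for confirmation ECGs either, unless the rise from baseline were at least 60 ms.
- Average 505 ms, repeat 490 ms: the 3-day rule is met by the first average. Section 5.6.2 is not met if the repeat governs (490 ms), nor if the two are averaged: (505 + 490)/2 = 497.5 ms.

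**Cross-reference.** Appendix 3 contains only renal alert criteria and actions, so it gives no QTc guidance.

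**Are the Table 5-6 times the full set of scheduled ECGs?** SAP Section 5.1.4 sets the upper limit of a window at the target plus the integer part of half the distance to the next target. It is written for days; applied to the listed ECG hours it gives:

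- KAE609: 4 + (12 − 4)/2 = 8; 12 + (24 − 12)/2 = 18; 24 + (52 − 24)/2 = 38; 52 + (60 − 52)/2 = 56; 60 + (72 − 60)/2 = 66.
- Coartem: 6 + (68 − 6)/2 = 37.

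All six match the table. An additional ECG in a gap would have moved a boundary: one at 28 h for KAE609 would give (24 + 28)/2 = 26 h instead of 38 h, and one at 24 h for Coartem would give (6 + 24)/2 = 15 h instead of 37 h.

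**ECGs against doses.** Nominal KAE609 doses at 0, 24 and 48 h are inferred from once-daily dosing. The ECG pattern fits: 52, 60 and 72 h are 4, 12 and 24 h after 48 h. The ECG footnote to Table 6-1 puts the ECG ahead of other procedures at the same nominal time, so the 24 h ECG is read as before dose 2.

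| Interval | Scheduled ECGs |
|---|---|
| KAE609 dose 1 to 2 (0–24 h) | 4, 12, 24 h |
| KAE609 dose 2 to 3 (24–48 h) | none |
| KAE609 after dose 3 | 52, 60, 72 h |
| Coartem dose 1 to 2 (0–8 h) | 6 h |
| Coartem dose 2 to 6 (8–60 h) | none |
| Coartem after dose 6 | 68 h |

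The gaps between ECGs are 52 − 24 = 28 h and 68 − 6 = 62 h. The permitted tolerances (±30 min up to 24 h, ±2 h from there to 72 h) do not close them. The earliest 52 h ECG is at 50 h, after dose 3 at 48 h, and the earliest 68 h ECG is at 66 h, after the last Coartem dose at 60 h.

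**Patients concerned.** KAE609 3-day arms: 10 + 20 + 20 = 50. Coartem: 6 cohorts × 10 = 60. Together 110 of the 210 planned.

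**The case against.** The best defence is that the passages can be read together. Section 5.6.2 lists reasons that compel stopping; it does not oblige anyone to continue, and it also leaves room for the investigator's judgment on safety. Section 6.5.5 adds a trigger for 3-day regimens, and a site that stops satisfies both. ECGs are taken in triplicate, so an average already rests on several tracings, and Section 6.5.5 does describe confirmation. This shows that the passages can be obeyed together and that confirmation is not absent from the section. It does not say whether confirmation precedes the stop, and the section itself treats confirmation as additional ECGs beyond the triplicate.

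A reader might infer that the 3-day rule lacks a correction formula because its sentence says only QTc. The documents do not support that: Section 6.5.5 prescribes Fridericia's correction for clinical decisions.

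On the schedule, Table 5-6 is an analysis table, and the ECG schedule itself is the Table 6-1 grid, which is not in the text reviewed. The midpoint check is strong but not proof, because the table does not follow its own rule everywhere. The PK window for 24 h also ends at 38 h although the next PK time is 48 h (midpoint 36 h); the SAP's Document History says a 36 h PK window was removed. The Coartem 68 h ECG window ends on Day 13, whereas Day 3 + (29 − 3)/2 gives Day 16. The gap is therefore probable and needs confirming.

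**Conclusion.** The inconsistency in the stopping rule stands on the text alone. At the limit it is narrow, confined to a value of exactly 500 ms. The substantive part is a single triplicate average against a repeat or confirmed reading. The wrong appendix reference adds to it. How often patients would be affected cannot be estimated from the documents.

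The schedule point stands as an inference about scheduled ECGs only. On those, the 3-day rule would act on dose-1 readings alone. A reader might go further and conclude that only a first-dose effect can ever trigger it. That is too strong: the rule covers any post-dose average, patients are inpatients until Study Day 4, and unscheduled ECGs remain possible.

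The firm count is 50 of 210 patients. The figure of 110 holds only if the 3-day regimens in Section 6.5.5 include Coartem, which the protocol does not state. The timing result also rests on nominal KAE609 doses at 0, 24 and 48 h, on the 24 h ECG preceding dose 2, and on Table 5-6 reflecting Table 6-1.

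**What to change.** Reconcile Protocol Sections 5.6.2 and 6.5.5 and Appendix 1 into one consistent statement that gives the limit and says whether confirmation precedes stopping. Correct the reference to Appendix 3. State whether the 3-day rule includes Coartem. Check the ECG rows of Table 6-1 against SAP Table 5-6, and reconcile the rule's scope with that schedule. The sponsor decides the content; this review takes no view on which limit, confirmation step or ECG timing is right.

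The cost is amendment wording and a check of one table. If the sponsor's reconciliation changes the schedule, the Table 5-6 windows must follow. Because the SAP history records an update after database lock, the study report should say which reading of the rule was applied to patients already treated.
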